3.2 Exclusion Criteria

- 3.2.1 Current General Inpatient (GIP) hospice status
- 3.2.2 Patients currently receiving chemotherapy
- 3.2.3 Condition impairing oral intake or digestive absorption
- 3.2.4 Presence of a delirium diagnosed by the CAM (see Appendix A)
- 3.2.5 Significant suicide risk as defined by suicidal ideation with intend and a plan as endorsed on item 5 on the C-SSRS within the past month or at V0 (see Appendix A)
- 3.2.6 Current or past history of schizophrenia, psychotic disorder, bipolar disorder, delusional disorder, paranoid personality disorder, schizoaffective disorder, or borderline personality disorder, as assessed by medical history
- 3.2.7 History of allergic reactions attributed to compounds of similar chemical or biologic composition to psilocybin
- 3.2.8 Other personal circumstances and behavior that would limit compliance with study requirements, or judged by the study psychiatrist and/or principal investigator to be incompatible with establishment of rapport or safe exposure to psilocybin
- 3.2.9 Potential for adverse drug-drug interactions. Concomitant medications with significant potential to interact with study medications will be exclusionary if they cannot be tapered. These include the following:
 - Serotoninergic antidepressants
 - Centrally-acting serotonergic agents (e.g. MAO inhibitors)
 - Antipsychotics (e.g. first and second generation)
 - Mood stabilizers (e.g. lithium, valproic acid)
 - Aldehyde dehydrogenase inhibitors (e.g. disulfiram)
 - Significant inhibitors of UGT 1A0 or UGT 1A10

Any psychiatric medication will be tapered if possible in an appropriate fashion to avoid withdrawal effects. They will be discontinued long enough before the psilocybin Session to avoid the possibility of any drug-drug interaction (the interval will be at least five times the particular drug and active metabolites' half-life). See section 9 of the protocol for concomitant medications and tapering instructions.

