5.2. Pre-Treatment Criteria

5.2.1. Cycle 1, Day 1

- Vital signs in the normal range
- Palliative Prognosis Score ≥ 50 %
- No significant suicide risk
- No delirium
- No contra-indicated medication

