Psilocybin is contraindicated in participants who are on monoamine oxidase inhibitors or who have a known sensitivity to the drug or its metabolites. It is contraindicated in medications that are known uridine diphosphate glucuronosyltransferase enzyme modulators. It is contraindicated in patients with schizophrenia or bipolar disease, or in those with first degree relatives with these disorders. The concurrent use of selective serotonin reuptake inhibitor/serotonin-norepinephrine reuptake inhibitors (SSRI/SNRI) medications is assumed to be contraindicated due to the potential to increase the risk of serotonin syndrome and/or to attenuate the binding of psilocin to the HT2A receptor.

Prior to enrollment participants will be screened per the clinical protocol for contraindicated psychologic conditions or interacting medications by a licensed physician on the study team.

Because there is a potential for interaction of psilocybin with other concomitantly administered drugs through the cytochrome P450 system, the study team will review the concurrent use of all other drugs, over-the-counter medications, or alternative therapies at every visit. The PI should be alerted if the participant is taking any agent known to affect or with the potential to affect selected CYP450 isoenzymes. Appendix C presents guidelines for identifying medications/substances that could potentially interact with the study agent(s).

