8.3. Description

Psilocybin is a tryptamine derivative. Its chemical name is [3-[2-(dimethylamino)ethyl]-1H-indol-4- yl] dihydrogen phosphate. The molecular structure is the following:

Figure 8.1-1: Molecular structure of psilocybin

Following oral administration (0.224 mg/kg) of psilocybin, average blood concentration of the active metabolite psilocin was calculated to be 8.2 ± 2.8 ng/mL after 105 ± 37 minutes, yielding an estimated dose-normalized bioavailability of psilocybin to be $52.7 \pm 20\%$ (N = 3). Psilocin typically appears in plasma within 15 minutes after oral administration. Psilocin half-life following oral administration of psilocybin was found to be approximately 3 ± 1.1 hours and is detectable for up to 24 hours after administration.^{3,4} The levels of psilocin peaked at approximately 80 minutes, but the peak psilocin concentration was more gradually attained in some subjects than in others, suggesting metabolism rates can vary between individuals.³

Psilocin is metabolized to 4-hydroxyindole-3-acetic acid by deamination and demethylation via liver enzymes such as monoamine oxidase, and aldehyde dehydrogenase (Figure 8.1-2).⁴ Psilocin is also extensively glucuronidated by the UDP- glucuronosyltransferase (UGT) family of enzymes, with the highest glucuronidation activity demonstrated by UGT1A10.⁷⁰ The amount of psilocin glucuronide-excreted renally has been shown to exceed that of psilocin over a 24-hr time period, and analysis of psilocin in urine over 24 hours after a single dose has shown that less than 4% of the overall clearance of psilocin occurs through renal excretion.⁷¹The pharmacokinetics of psilocybin (as psilocin) are linear over the dose range of 0.3–0.6 mg/kg.^{3,71}

Figure 8.1-2: Metabolism of psilocybin

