9. CONCOMITANT MEDICATIONS AND TAPERING INSTRUCTIONS

If the participant is being treated with psychiatric drugs at the time they are recruited into the study, they will discuss medication tapering with the study psychiatrist and the hospice physician. If needed, the drugs will then be tapered in an appropriate fashion to avoid withdrawal effects. They will be discontinued long enough before the first Experimental Session to avoid the possibility of any drug-drug interaction (the interval will be at least five times the particular drug and active metabolites' half-life).

The therapists will request information about any changes in medication just prior to all intervention sessions. The study psychiatrist will be responsible for reviewing and confirming all medications collected during the study.

All medications, over the counter (OTC) and prescription will be collected from screening through V5. Throughout the protocol all medications used to treat AEs will be collected and all changes including discontinuations or additions to psychiatric medications will be collected. Medications will be recorded on the concomitant medications CRF.

In general, any MAOi will require a washout of at least 14 days or five half-lives of the medication or active metabolite (whichever is greater) plus one week for symptom stabilization. The Medication Tapering Table includes phenelzine, an example MAOi, (half-life of 11.6 hours) with a minimum of 14-day washout as requested. However, this table is not exhaustive. The washout time for any drug not listed on the table will be at least 5 times the half-life of the drug or active metabolite, plus 1 week for symptom stabilization.

Participants must be willing to refrain from taking any contra-indicated psychiatric medications during the active portion of the study.

As we expect individuals on hospice to be receiving medications to control symptoms such as pain, nausea and anxiety, all efforts will be made to not disrupt a patient's medication regimen unless the medication is contraindicated or carries a risk of interfering with psilocybin. Medications, such as opioids, may be given to patients during the trial to control pain, with efforts being made to not administer medications during the peak effect of psilocybin.

Medication Tapering Table

Version Date: April 18, 2023

Generic Name	Brand Name	Half-life (hours)	Days for Washout
		Including Active Metabolites	
alprazolam	Xanax	11	3
aripiprazole	Abilify	75	16

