atomoxetine	Strattera	5-24	5
bupropion	Wellbutrin	21	5
citalopram	Celexa	35	8
clonazepam	Klonopin	30-40	8
diazepam	Valium	20-70	15
duloxetine	Cymbalta	12	3
escitalopram	Lexapro	32	7
fluoxetine	Prozac	7-9 (days)	45
imiprimine	Tofranil	6-18	4
lamotrigine	Lamictal	25	6
lorazepam	Ativan	12	3
mirtazapine	Remeron	20-40	8
olanzapine	Zyprexa	21-54	11
paroxetine	Paxil	21	5
phenelzine	Nardil	11.6	14
prazosin	Minipress	2-3	1
quetiapine	Seroquel	6	2
risperidone	Risperdal	3-20	4
sertraline	Zoloft	26	6
temazepam	Restoril	8-12	3
trazodone	Desyrel	9	2
venlafaxine	Effexor	12	3
ziprazidone	Geodon	7	2
zolpidem	Ambien	2.5	<1

The PI may prescribe a designated rescue medication in the event of symptoms that require it during or after the Experimental Session (e.g. insomnia or severe anxiety that does not respond to other non-pharmacologic management outlined in the treatment manual). Rescue medications may be a benzodiazepine, zolpidem, or other anxiolytic or sedative according to the physician's clinical judgment. SSRIs, SNRIs, and MAOIs should not be used as rescue medications.

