11. STUDY CALENDAR

11. ST UD		DAK							
	Full screenning + enrollment	Preparation session 1	Preparation session 2	Psilocybin session	Integration session 1 (Day 1)	Integration session 2 (Day 7)	F/U (HOME)	EDC Timepoints	
Visit	VO	V1	V2	V3	V4	V5	V6a,b,,f		
Timing	At least 48h prior to the psilocybin session (V3)	Baseline ≤3 weeks prior to Day 0	≤7 days prior to Day 0	Day 0	Day 1	Week 1 Day 7	Week 3 Monthly after Week 3 Until Week 24 or death	N/A	
Allowable Window					Up to Day 3	Up to Day 14	±14 Day		
Location	Home/Remote	Home/Remote	Home/Remote	Hospice	Home/Remote	Home/Remote	Home/Remote		
Psilocybin				25 mg				V3	
Psychotherapy - min (staff)		60 (LT-CT)	60 (LT-CT)	7h30 (LT-CT)	60 (LT-CT)	60 (LT-CT)		Psychotherapy notes should be captured after V1, V2, V3 V4 and V5	
Assessment - min (staff)	60 (LT-RA)	30 (LT-RA)	15 (LT-RA)	30 (LT-RA)	15 (LT-RA)	30 (LT-RA)	30 (RA)	N/A	
			Clinic	al Assessments and Proced	lures				
Informed consent patient	√							N/A	
Informed consent cargiver	√							N/A	
Demographics	√							V0	
Medical and psychiatric history	√							V0	
Inclusion/exclusion criteria	√							V0	
PPS	√	✓	√	√	√	√	√	During all visits	
САМ	√	✓	√	√	√	√		V0, V1, V2, V3, V4, V5	
C-SSRS (1)	√	✓	√	✓	✓	√		V0, V1, V2, V3, V4, V5	
Vital signs (2)	√			✓				V0, V3	
Physical examination (2)	√			√				V3	
Prior/concomitant medication	√	✓	√	√	√	√		N/A	
Medication taper (if applicable)	√	√	√					NA	
AE/SAEs		✓	√	√	√	√	√	During all visits	
Session recording		✓	√	√	√	✓		NA	
Qualitative interview patient						✓		NA	
Qualitative interview caregiver (3)						√		NA	
Qualitative interview hospice staff							✓	NA	
nospice stan			Particip	pant Completed Assessmen	nts (8)				
DS-II	✓	✓	√	✓	√	√	√	During all visits	
HADS A and D (4)		√	✓	√	√	✓	√	During all visits	
FACIT-Pal 14		✓				√	√	V1, V5, V6a,b,,f	
PIS (6)		✓				√	√	V1, V5, V6a,b,,f	
LAP-R		✓				√	√(7)	V1, V6a	
SIS		√				√	✓	V1, V5, V6a,b,,f	
FACIT-sp		√				✓	✓	V1, V5, V6a,b,,f	
MEQ-30 (5)				✓				V3 or V4	
CEQ (5)				√				V3 or V4	
SAHD		√				✓	√(7)	V1, V6a	
RRPQ						√		V4 or V5	
CarGOQoL (3)		✓				√	√	V1, V5, V6a,b,,f	
Abbreviations IT: Lead Ther		1 1 1 1 1 1 1 1 1 1 1 1 1 1 1 1 1 1 1 1			1	10 : 510/70 !		L	

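### The tapering table prints 14 days for phenelzine where section 9 requires 21 with its symptom-stabilization week, and tapering allowed after V1 can blur change from baseline

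*Combined protocol and SAP*

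**What the plan says.** **Washout rules.** Section 3.2.9 sets the general floor in half-lives: "the interval will be at least five times the particular drug and active metabolites". Section 9 repeats it and adds that an MAO inhibitor "will require a washout of at least 14 days or five half-lives of the medication or active metabolite (whichever is greater) plus one week"; the sentence goes on to say that the week is for symptom stabilization. For drugs not in the table, section 9 requires five half-lives plus the same week and counts that week as part of the washout time.

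**The table.** Section 9 introduces the phenelzine row this way: "The Medication Tapering Table includes phenelzine, an example MAOi, (half-life of 11.6 hours) with a minimum of 14-day washout as requested". The row prints 14 days. The dosing-day check in section 5.2.1 reads "No contra-indicated medication" and gives no interval.

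**Timing against the baseline.** Sections 3.2.9 and 9 tie the interval to the psilocybin session only. The Study Calendar (section 11) puts V1 at most 3 weeks and V2 at most 7 days before Day 0, and ticks medication taper at V0, V1 and V2. Section 13.3.3 defines each secondary efficacy endpoint as change from V1, with comparisons at the 0.05 level and no split by taper status. It also plans descriptive summaries of all efficacy scores at all visits.

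**Scores taken before the dose.** The calendar has DS-II at V0 to V3 and HADS at V1 to V3. Section 5.1.2 confirms that the V3 scores precede dosing. The DS-II and HADS headings in section 5.1.5 list only V1, V5 and V6.

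**The concern.** Staff have two numbers for the same drug. The rule in the text leads to 21 days and the table prints 14. Nothing at the table or in the dosing-day check tells the reader to add a week. An unlisted MAO inhibitor with the same half-life would wait 21 days. A patient cleared from the table could be dosed a week before the protocol's own stabilization period has ended.

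The baseline question is separate and does not depend on phenelzine. Nothing requires the last dose of a tapered drug to come before the V1 scores. A patient may therefore score V1 on a drug and V5 off it. If stopping worsens symptoms, change from V1 understates any benefit. If V1 falls in a withdrawal period that has settled by V5, it overstates benefit. Section 13.3.1 uses the effect size from this study to plan the confirmatory trial.

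**Working it through.** **Phenelzine.** Inputs from section 9: half-life 11.6 h, minimum 14 days, additional week 7 days.

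- Five half-lives: 5 × 11.6 / 24 = 2.42 days.
- Drug washout: max(14, 2.42) = 14 days. This reproduces the printed figure.
- Full rule: max(14, 2.42) + 7 = 21 days, which is 7 more than printed.
- The only grouping that keeps 14 is max(14, 2.42 + 7) = max(14, 9.42) = 14. The text states the choice of the larger value before it adds the week, so this is a strained reading.

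**Other rows.** Five times the upper printed half-life, rounded up to whole days, equals the printed value in 21 of the 25 other rows (zolpidem is 0.52 days, printed as under 1). The four exceptions are:

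| Drug | Upper half-life (h) | 5 × half-life (h) | Printed days (h) | Short by | Rounded up |
|---|---|---|---|---|---|
| Clonazepam | 40 | 200 | 8 (192) | 8 h | 9 |
| Mirtazapine | 40 | 200 | 8 (192) | 8 h | 9 |
| Olanzapine | 54 | 270 | 11 (264) | 6 h | 12 |
| Risperidone | 20 | 100 | 4 (96) | 4 h | 5 |

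**Last dose relative to V1 and V2.** With V1 at Day −21, a drug with a washout of d days can be taken until 21 − d days after V1.

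- As printed, 25 of 26 rows have d of 16 or less (all but fluoxetine, 45), so the last dose can follow V1.
- With the five rows corrected, 24 of 26 still can. Phenelzine would stop on the day of V1.
- With V2 at Day −7, 18 of 26 rows have d of 7 or less, so the drug can still be taken at V2.

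**What the pre-dose V3 score can show.** At V3 the drug has been stopped, but the recall period can reach back to days on it. With the corrected table, 22 of 26 rows have d below 14 (all but aripiprazole 16, diazepam 15, fluoxetine 45 and phenelzine 21), so DS-II's two-week recall can include such days. For the one-week HADS recall (d below 7) the count is 17 of 26. Six patient scales (FACIT-Pal 14, PIS, LAP-R, SIS, FACIT-sp, SAHD) have no pre-dose value except V1.

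**The case against.** **On phenelzine.** The washout column may be meant to show drug clearance only, with the stabilization week added on top. No row contains that week, and the text calls 14 a minimum. The study psychiatrist also discusses each taper and confirms all medications, so the table is not the only safeguard. This explains the 14 but does not remove the mismatch: the table does not say so, and for unlisted drugs section 9 counts the week as washout time.

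**A stronger safety reading.** A reader might infer that the table exposes phenelzine patients to a drug interaction. Section 8.3 says psilocin is broken down "by deamination and demethylation via liver enzymes such as monoamine oxidase", section 5.4 states that "Psilocybin is contraindicated in participants who are on monoamine oxidase inhibitors", and section 9 adds that "SSRIs, SNRIs, and MAOIs should not be used as rescue medications". The documents do not support that inference. Both the 14-day and the five-half-life requirements are met at 14 days, and the missing week is labeled as being for symptoms. Nor do they show that every row is a week short: section 9 attaches the week to MAO inhibitors and to unlisted drugs.

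**On rounding.** The shortfalls are hours and arise only at the top of each half-life range. At the midpoint all four printed values exceed five half-lives (clonazepam at 35 h: 7.3 days against 8). The written floor also applies whatever the table prints. That makes the point minor but leaves the correction worth making.

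**On the baseline.** Efficacy is secondary in a 15-patient single-arm pilot, and change from V1 already includes preparation, expectancy and disease course. DS-II and HADS are collected at V2 and V3, and the all-visit summaries in section 13.3.3 would cover them. This stands. What remains missing is a change from the last pre-dose score and a split by taper status. The per-protocol set does not supply one, since a taper that follows the protocol is not a deviation.

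**Conclusion.** The concern holds with limits. Section 9 requires 21 days for phenelzine and the table prints 14. The 7-day shortfall is in the protocol's own stabilization period, not in the drug washout. Four further rows fall 4 to 8 hours below the five-half-life floor if the upper printed half-life is used.

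Change from V1 can mix drug withdrawal with psilocybin in patients whose taper runs past V1. The printed washouts permit this for 25 of 26 listed drugs when V1 is at Day −21. That count shows what the plan permits, not how often it will happen. The documents do not say how many recruits will taper or how far stopping moves the scores, so a reader who infers a demonstrated bias in the efficacy results goes beyond them. The feasibility and acceptability benchmarks do not use change from V1 and are not affected.

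**What to change.** 1. In section 9, print 21 (14 + 7) in the phenelzine row and in the sentence that cites it. Print clonazepam 9, mirtazapine 9, olanzapine 12 and risperidone 5.
2. Keep V1 as the baseline. In section 13.3.3 add a supplementary descriptive summary of DS-II and HADS change from the pre-dose V3 score, shown with the V2 scores already collected. List individual values by taper status, defined as any psychiatric drug with a last dose or dose reduction after V1, taken from the concomitant medications CRF. Flag those patients on the six scales whose only pre-dose value is V1.
3. Align the section 5.1.5 headings with the calendar: DS-II V0 to V6, HADS V1 to V6.
4. Report these results beside the V1 effect size used to plan the confirmatory trial.

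**Cost.** Five table cells, one sentence, one analysis paragraph and two headings, with no new visit, measure or CRF field. Phenelzine patients wait 7 days longer than the table says, though no longer than the text requires. Patients on the four rounded drugs wait 1 day longer.

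For scale, assume exponential survival, so that the loss over d days is 1 − 2^(−d/median). Section 13.3.1 gives a median of 43 days or more for PPS 50 and above; half and double that are shown as a range.

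| Median (days) | Lost over 7 days | Lost over 1 day |
|---|---|---|
| 21 | 20.6% | 3.2% |
| 43 | 10.7% | 1.6% |
| 86 | 5.5% | 0.8% |

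PPS 40 is eligible, and decline short of death also stops dosing, so true losses could be higher than the 43-day row. The V3 score follows both preparation sessions and its recall can still include on-drug days, so it supplements V1 and does not replace it.

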10. RISKS AND MITIGATION STRATEGY IN RESPONSE TO THE SARS-COV2 PANDEMIC

Care Dimensions has taken the following steps to ensure the safe delivery of care:

- Additional mandatory staff education on infection prevention procedures, the COVID-19 virus, and Care Dimensions precautions and procedures, so all staff have the latest information.
- Employees and volunteers are required to stay home when feeling sick. They must be fever free for 24 hours before returning to work.

Employees and volunteers are being strongly discouraged from travelling internationally. Those returning from a CDC Level 3-defined country or certain US communities with widespread ongoing disease and travel restrictions may not return to work or see patients until 14 days after their return.

- Employees and volunteers who have had prolonged close contact to someone with confirmed or presumed diagnosis with COVID-19 or who has traveled to the countries or communities listed above, must report this to their manager to assess whether they need to self-quarantine for 14 days.
- Employees are not permitted to attend any conferences and have been instructed to avoid large public gatherings.
- Patient visits in most facilities have been reduced to nurses, social workers, chaplains, and hospice aides to comply with DPH guidelines.
- Working with each hospital and nursing facility to comply with their individual regulations and screening of our staff.
- Visitors to the hospice houses (in particular the Care Dimensions Hospice House in Lincoln where V3 of this study occurs) have been restricted to immediate family members (as defined by the patient) only, with a maximum of 2 visitors at at time and 6 per patient, per day. Visitors are screened upon entrance for temperature, symptoms and potential COVID-19 exposure to assess need for further precautions, and must wear a mask at all times while in the hospice house. Common areas of the houses are closed and visitors must stay in patient rooms.
- Cleaning services at our offices and hospice houses include enhanced disinfection of all high-touch surfaces such as doorknobs, handles, counters and railings and common equipment.
- All in-person support groups, trainings and meetings with non-staff members at our facilities have been suspended. Some support groups have started to meet online.
- Routine work-related meetings are being held virtually with video and teleconferencing and staff are prohibited from working at more than one Care Dimensions location.
- Care Dimensions equips clinical staff with a supply of hand sanitizer, anti-bacterial wipes and personal protective equipment (PPE) such as masks, gowns and goggles.
- Care Dimensions has a comprehensive Emergency Operations Plan, which has been activated and will be amended as this crisis response progresses.

In order to mitigate the risk of SARS-CoV-2 virus transmission during the study, the Principal Investigator, Study Team Members, and Study Subjects will adhere to Care Dimensions

guidelines. All study activities that don't necessitate in-person interaction with patients, families and/or staff, or within the study team, will be conducted remotely.

11. STUDY CALENDAR

11. ST UD		DAK							
	Full screenning + enrollment	Preparation session 1	Preparation session 2	Psilocybin session	Integration session 1 (Day 1)	Integration session 2 (Day 7)	F/U (HOME)	EDC Timepoints	
Visit	VO	V1	V2	V3	V4	V5	V6a,b,,f		
Timing	At least 48h prior to the psilocybin session (V3)	Baseline ≤3 weeks prior to Day 0	≤7 days prior to Day 0	Day 0	Day 1	Week 1 Day 7	Week 3 Monthly after Week 3 Until Week 24 or death	N/A	
Allowable Window					Up to Day 3	Up to Day 14	±14 Day		
Location	Home/Remote	Home/Remote	Home/Remote	Hospice	Home/Remote	Home/Remote	Home/Remote		
Psilocybin				25 mg				V3	
Psychotherapy - min (staff)		60 (LT-CT)	60 (LT-CT)	7h30 (LT-CT)	60 (LT-CT)	60 (LT-CT)		Psychotherapy notes should be captured after V1, V2, V3 V4 and V5	
Assessment - min (staff)	60 (LT-RA)	30 (LT-RA)	15 (LT-RA)	30 (LT-RA)	15 (LT-RA)	30 (LT-RA)	30 (RA)	N/A	
			Clinic	al Assessments and Proced	lures				
Informed consent patient	√							N/A	
Informed consent cargiver	√							N/A	
Demographics	√							V0	
Medical and psychiatric history	√							V0	
Inclusion/exclusion criteria	√							V0	
PPS	√	✓	√	√	√	√	√	During all visits	
САМ	√	✓	√	√	√	√		V0, V1, V2, V3, V4, V5	
C-SSRS (1)	√	✓	√	✓	✓	√		V0, V1, V2, V3, V4, V5	
Vital signs (2)	√			✓				V0, V3	
Physical examination (2)	√			√				V3	
Prior/concomitant medication	√	✓	√	√	√	√		N/A	
Medication taper (if applicable)	√	√	√					NA	
AE/SAEs		✓	√	√	√	√	√	During all visits	
Session recording		✓	√	√	√	✓		NA	
Qualitative interview patient						✓		NA	
Qualitative interview caregiver (3)						√		NA	
Qualitative interview hospice staff							✓	NA	
nospice stan			Particip	pant Completed Assessmen	nts (8)				
DS-II	✓	✓	√	✓	√	√	√	During all visits	
HADS A and D (4)		√	✓	√	√	✓	√	During all visits	
FACIT-Pal 14		✓				√	√	V1, V5, V6a,b,,f	
PIS (6)		✓				√	√	V1, V5, V6a,b,,f	
LAP-R		✓				√	√(7)	V1, V6a	
SIS		√				√	✓	V1, V5, V6a,b,,f	
FACIT-sp		√				✓	✓	V1, V5, V6a,b,,f	
MEQ-30 (5)				✓				V3 or V4	
CEQ (5)				√				V3 or V4	
SAHD		√				✓	√(7)	V1, V6a	
RRPQ						√		V4 or V5	
CarGOQoL (3)		✓				√	√	V1, V5, V6a,b,,f	
Abbreviations IT: Lead Ther		1 1 1 1 1 1 1 1 1 1 1 1 1 1 1 1 1 1 1 1			1	10 : 510/70 !		L	

Abbreviations. LT: Lead Therapist; CT: Co-Therapist; PA. Research Assistant; DS-H: Demoralization Scale-II; HADS A and D: Hospital Anxiety and Depression Scale Anxiety and Depression; FACIT-Pal 14: Functional Assessment of Chronic Illness Therapy Palliative Care 14; PIS: Pain Interference Scale; LAP-R: Life Attitude Profile – revised, Death acceptance subscale; SIS: Social Isolation Scale; FACIT-Sp 12: Functional Assessment of Chronic Illness Therapy-Spiritual Well-Being 12; MEQ-30: Mystical Experience Questionnaire; CSQ: Challenging Experience Questionnaire; SAMD: Schedule of Attitude toward Hastened Death; C-SSRS: Columbia-Suicide Severity Rating Scale; CAM: Confusion Assessment Method; PPS: Palliative Performance Scale; RRPQ-R: Reactions to Research Participation Questionnaire Revised; CarGOQoL: CareGiver Oncology Quality of Life questionnaire.

(1) The "Last month" version will be administered at Screening (V1) and the "Since Last Visit" version will be administered at all other visits.

⁽a) Lares lever only
(d) These assessments will also be completed by the participant's cargiver at V1, V5 and V6a,...f
(e) Only if the patient indicates pain at a given assessment period.
(f) Only at V6a
(g) We anticipate that given their terminal condition, participants might not be able to complete these questionnaires or may only be able to complete part of them. To reduce administrative burden, we will not report those missing questionnaires as protocol violations.

